1.0 Background

The novel coronavirus known as SARS-CoV-2 and the associated disease process COVID-19 (coronavirus disease 2019) was first seen in late 2019 in Wuhan, China. Over the following months, it quickly spread across the continent and, in short order, the globe, making an impact that hasn't been seen in generations. Although coronaviruses have been prevalent for millennia, this version is immunologically novel, and thus there is no natural immunity to the virus. This has been a major reason for its rapid spread across the world.

Previous members of the coronavirus family have typically caused upper respiratory symptoms such as the common cold, though there have also been more virulent versions of this virus seen in the recent past, such as SARS (Severe Acute Respiratory Syndrome) and MERS (Middle East Respiratory Syndrome). Similarly named, SARS-CoV-2 also causes upper respiratory symptoms but has varied from the previous viral syndromes in a number of ways including how quickly it has been able to transmit within a population. This is a disease that does not segregate and can affect all ages, genders, and ethnicities. Everyone is susceptible to this virus.

New diagnostic and therapeutic approaches for respiratory viruses are also being rapidly developed and polymerase chain reaction-based (PCR) diagnostics and multiplex assays are increasingly used in clinical laboratories for SARS-CoV-2 clinical detection and subtyping. Rapid antigenic and genetic evolution has been expected for SARS-CoV-2 strains, and a better understanding of SARS-CoV-2 evolutionary dynamics is needed to establish an effective vaccine.

Our present understanding of the nature and extent of the upper respiratory track (URT) microbiome in humans is limited. Furthermore, we have little understanding of how acute viral respiratory infections of SARS-CoV-2 influence the URT microbiome, or how genotypic differences in the virus influence the URT microbiome and vice versa. Innate immune responses to pathogens, along with dysregulation of inflammation, are key factors involved in pathogenesis, and different viral pathogens activate different types of inflammatory responses. Respiratory viral infection i.e., SARS-CoV-2 infection is expected to activate TLR2, TLR3, TLR4 and TLR7 responses and this is likely to modulate commensal microbiota populations. It is not yet known if the severity of SARS-CoV-2 disease in older adults is due to a biased host response, SARS-CoV-2 virulence determinants, or the impact infection has on commensal microbiota.

Up to this point, there is no unanimously approved treatment for the disease nor is there a vaccine or antiviral drugs available for the public. The primary methods for treatment of this deadly virus have been supportive in nature including intubation in severe cases with respiratory failure.

While a unanimous treatment has yet to be discovered, there has been a great amount of knowledge garnered over the last few months about the virus and the disease that accompanies it. Several studies have demonstrated high viral titers within the nasopharynx and oral cavity and many have posited that this is the primary source of infection and viral replication. Additionally, a high nasal/nasopharyngeal viral load has been associated with increased symptoms and higher severity of the disease.

Interestingly, there have been a number of studies recently looking at the effect of nasal saline irrigations in the setting of viral URIs, including coronaviruses (not including SARS-CoV-2). One of the major takeaways from these studies was decreased viral shedding in patients treated with saline irrigations compared to the control group. Nasal saline irrigations are available over the counter and widely viewed as both safe and affordable. Could these irrigations have a similar effect on the novel SARS-CoV-2 that they have on other viral respiratory infections?

2.0 Rationale and Specific Aims

While many systemic medications and treatments have been proposed, there has not yet been a study looking at targeted local intervention to the nasal cavity and nasopharynx where the viral load is the highest. Studies have shown that the use of simple over the counter nasal saline irrigations can decrease viral shedding in the setting of viral URIs, including the common coronavirus (not SARS-CoV-2). Further, as SARS-CoV-2 is an enveloped virus, mild-detergent application with nasal saline would neutralize the virus further. It is our hypothesis that nasal saline or nasal saline with baby shampoo irrigations may decrease viral shedding/viral load and viral transmission, secondary bacterial load, nasopharyngeal inflammation in patients infected with the novel SARS-CoV-2.

Specific Aim 1. Define the longitudinal SARS-CoV-2 mucosal immune response, microbial load, and viral load in the nasopharynx over the course of COVID-19 infection.

Specific Aim 2. Assess the impact of nasal saline or nasal saline with baby shampoo on SARS-CoV-2 viral load, mucosal inflammation and secondary bacterial load in nasal cavity.

Specific Aim 3. Identify the longitudinal symptom burden and temperature during the course of the disease

3.0 Animal Studies and Previous Human Studies

Nasal saline irrigations are a safe and commonly used mechanism to treat a variety of sinonasal diseases including sinusitis, rhinitis, and upper respiratory tract infections. When used properly, these irrigations are a safe and easy intervention available over the counter without a prescription. Additionally, baby shampoo has been found to be a safe additive functioning as a surfactant when a small amount is added to the saline rinses which may help augment clearance of the sinonasal cavity.

There have been reports of infections secondary to improper use and thus it is important to use filtered water or previously boiled water when performing rinses. Apart from these issues related to improper use, there are no substantial adverse effects associated with nasal saline irrigations noted in prior human studies. Typically, nasal saline irrigations have been a treatment in prior studies as a part of the control arm assessing intranasal medications, but there are no discrete Phase 1, 2, or 3 studies looking at nasal saline as an independent intervention, as nasal saline rinses have for many years been used as a standard care adjunct for intranasal/sinus disease. There have been a small number of studies showing a transient loss of smell when adding surfactant to nasal saline rinses, though this appears to resolve when surfactant is discontinued.

4.0 Inclusion/Exclusion Criteria

List the criteria:

- Inclusion
 - Patients testing positive for COVID-19 at Vanderbilt University Medical Center or VUMC-associated testing centers
 - Age of 18 years or greater
 - Patients must be planning self-quarantine after infection in the greater Nashville area within a 30-mile radius of Vanderbilt University Medical Center
- Exclusion
 - Requiring hospitalization only outpatient COVID-19 cases are eligible for the study
 - Current use of nasal saline irrigations or other intranasal medications
 - Inability to perform saline irrigations/nasal swabs in separate bathroom away from household contacts

5.0 Enrollment/Randomization

Patients enrolled will be randomized to one of three treatment groups (control- no intervention, intervention 1- nasal saline irrigations BID, intervention 2- nasal saline irrigations with 1/2 teaspoon surfactant (Johnson's baby shampoo) BID). Patients identified as COVID-19 positive through VUMC testing centers will be contacted and given information regarding the study. Randomization, enrollment, and registration will take place via REDCap (*see telephone script*).

The address for the home of the study is:

Department of Otolaryngology – Head and Neck Surgery Vanderbilt University Medical Center [name]

Protocol Version #: 001 Protocol Date: March 30, 2020

6.0 Study Procedures

Day 0: Patient tests positive for COVID-19 via nasal swab which is identified through Epic and is given information about the trial via telephone call. At that time, they may determine whether or not they would like to be enrolled in the study. Those enrolled in the study will be randomly assigned into one of 3 groups (control, intervention 1, intervention 2) using REDCap and delivered a package containing: nasal swabs with premeasured depth for insertion, saline rinse bottle with saline packets and detailed instruction guide (intervention 1, 2), Johnson's Baby Shampoo (Johnson & Johnson Inc., New Brunswick, NJ) for use with saline rinses (intervention 2), and symptom questionnaire/temperature sheets.

Days 1-21: Patients in intervention group 1 and 2 will perform nasal saline irrigations +/- ½ teaspoon of Johnson's Baby Shampoo in the morning and the evening. All patients will perform nasal swabs every 2-3 days (*See Instruction Sheet*). In the intervention arms, these swabs should be taken at least 4 hours after saline rinses are performed. Patients will also check temperature (at same time each day) and fill out a symptom questionnaire (*See Symptom Questionnaire*). At the completion of week 3, patients will call our team to collect swabs and questionnaire/temperature sheets. The paper questionnaires will be transferred to REDcap for data collection and analysis.

*The timing of the study is based on when patient initially tests positive for COVID-19 and is a rolling enrollment rather than simultaneously performed.

Once 90 (~30 per group) patients have completed their 21 days of swabs/temperature checks/questionnaires, the study trial will be completed and data analysis will be performed. Interim analysis will be performed at 45 total patients.

As these patients will be under quarantine for COVID-19 infection, they will receive and provide their swabs, temperature and symptom scoring sheets from their home address at the beginning and at the conclusion of the 21-day study period. The swabs will be collected using OMR 110, DNA Genoteck Inc, Canada, that will immediately neutralize virus due to isotonic detergents present in the buffer, at the same time stabilizing the DNA and RNA for further analysis. Study administrators will wear appropriate personal protective equipment when retrieving the above-mentioned specimens.

Laboratory and Analytic Methods

qPCR Analysis to asses viral copy number: Viral RNA will be extracted using a standard Qiagen viral RNA isolation kit. After viral RNA extraction, qPCR will be utilized to analyze viral titers.

SARS-CoV-2 Complete Genome Sequencing and analysis: Viral RNA will be extracted using a standard Qiagen viral RNA isolation kit. We have established a high-throughput CoV genome sequencing pipeline, where we will perform overlapping long-range RT-PCR across the viral genome for each viral genome proposed in this project.

The sequencing will be performed using the Illumina MiSeq platforms. We will 1) generate the long-range amplicons; 2) create libraries; 3) perform high-throughput sequencing; 4) deconvolve and assemble sequencing reads; 5) close genomes using the appropriate finishing methods; and 6) submit the assembled sequence files and metadata to NCBI. We will apply phylodynamic analyses that are being developed as part of our analytic pipeline toward a comprehensive study of SARS-CoV-2 evolutionary dynamics. Genome sequences from these samples will allow us to assess the evolution and extent of co-circulation of the different SARS-CoV-2 subgroups; we will also assess whether there are genetic associations with different clinical signs and symptoms of disease severity using the vast amount of clinical metadata that are being collected. Because all sequence information will be made publicly available, this data will be of use for the entire SARS-CoV-2 research community and will serve as references for viral diversity for all subsequent studies in this field.

16S Sequencing for microbiome analysis: DNA/RNA isolation and 16S sequencing will be conducted as described before (2, 3). Microbial sequence data will be evaluated in the context of SARS-CoV-2 infection status to determine taxonomic profiles and their distributions within and between samples, including taxonomic classification and abundance, clustering, and measures of within sample (alpha diversity) and between sample (beta diversity) variation (4). Our goal is also to apply hypothesis testing for differences in community structure using multivariate statistics such as non-parametric multivariate analysis of variance (NP-MANOVA) and to estimate the significance of changes in the diversity, intragroup variation, and specific proportions of taxonomic classifications and OTUs. We will determine if specific microorganisms correlate with viral SNPs, disease severity, and/or host gene expression, especially genes important to innate immune response.

Metatranscriptomics Sequencing: To simultaneously sequence the viral, host, and microbial transcriptomes, RNA-seq libraries will be created from total RNA extracted from NP and oropharyngeal swabs and treated to remove all ribosomal RNA (Ribo-Zero[™], Epicentre). Forty-eight samples will be multiplex per lane on an Illumina NovaSeq V4 sequencing lane to producing ~10GB of 150-bp paired-end reads/sample. Based on our current experience with *de novo* metatranscriptomics assembly, we favor Trinity assembly software (5) for this project because it consistently predicted the longest and fewest number of contigs and had the highest rate of ORFs that align to known genes. Transcripts will be mapped onto risk-active genomes and their relative abundance determined from the various samples and time points. To validate RNA-seq data, we will perform qRT-PCR on selected genes that show specific differential expression patterns. Transcripts that correlate with host and microbiome responses in the samples selected for RNA-seq will be investigated across the entire sample set using qRT-PCR. The innate immune response data will be validated by examining the levels of cytokines and chemokines using Luminex assays.

Data integration. We will interrogate the taxonomic composition of the URT microbiome across a wide range of donors (from adults vs. infants) for which we will know the genome sequence of the infecting virus, the disease-severity phenotype, and the microbial diversity. These data will inform us as to the presence and relative abundance of key microbial species that reflect healthy versus disease states.

Incorporating RNA-seq data will provide insights into the active functions of the host and the microbiome (i.e., both taxonomy and function), including potential changes in expression caused by the infecting virus. Correlations between biomarker diversity profiles (e.g., 16S) and functional profiles (RNA-seq), along with disease phenotypes and relevant patient metadata, will be identified using statistical approaches. Distance matrices will be computed among the phenotypes that are ordinal and matrix regressed in conjunction with the distance matrices between the samples. Significance and effect sizes of the regression coefficients will be reported. Multiple regression will then be performed with all the biomarker and RNA-seq data types simultaneously, using each omics distance matrix as a predictor variable against the phenotype distance matrix as the response variable. The integration of these data will allow us to draw a more concrete picture of host-microbiome interactions, particularly as they relate to immune status and disease during SARS-CoV-2 infection.

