10.0 Statistical Considerations

As this is a pilot study for the use of nasal saline irrigations in the COVID-19 patient population, a true power analysis is not possible. This study will use a truncated initial sample size of 90 patients spread across 3 intervention arms to ensure that exclusion of true outliers is possible. Data will be analyzed with routine statistical software, with a planned 95% confidence interval for statistical testing.

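### The available text secures no quantified viral-load swab before the first rinse; a pre-rinse swab in all three arms, used as a covariate, could make the Aim 2 comparison more precise

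*Combined protocol and SAP*

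**What the plan says.** Aim 2 (section 2.0) is to "Assess the impact of nasal saline or nasal saline with baby shampoo on SARS-CoV-2 viral load", along with inflammation and bacterial load. Section 6.0 gives these facts on measurement:

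- **Day 0.** "Patient tests positive for COVID-19 via nasal swab which is identified through Epic". The text does not say that this specimen is quantified. The laboratory subsection says "qPCR will be utilized to analyze viral titers" and names no baseline time point.
- **Kit.** Study swabs reach the patient after randomisation, in the same package as the rinse materials.
- **Days 1-21.** Rinse arms irrigate morning and evening. "All patients will perform nasal swabs every 2-3 days", with a pointer to an Instruction Sheet that is not in the documents. The day and hour of the first swab are not given.
- **Order of rinse and swab.** "In the intervention arms, these swabs should be taken at least 4 hours after saline rinses are performed".
- **Logistics.** Materials are delivered and retrieved "from their home address at the beginning and at the conclusion of the 21-day study period". The collection buffer neutralises virus, "at the same time stabilizing the DNA and RNA for further analysis".

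Section 10.0 calls the study a pilot for which "a true power analysis is not possible". It names no model and no covariate for viral load.

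**The concern.** Patients found through routine testing will differ widely in viral load when they start, and later swabs will carry part of that difference. A load measured before treatment and used as a covariate removes the part it predicts from the error term. The text does not secure such a measurement: the Day 0 swab is a diagnostic result, and the only ordering rule for study swabs places them after a rinse in the two active arms. With about 30 patients per arm, the lost precision may be worth recovering. A baseline not collected before the first rinse cannot be obtained later.

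**Working it through.** **Inputs from the documents.** 90 patients in three arms: 90/3 = 30 per arm, which agrees with section 6.0. The 95% confidence level is in section 10.0. No power, effect size or SD is stated, so there is no power figure to reproduce.

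**Assumptions.** One pairwise comparison, two-sided 0.05, 80% power, equal variances, complete and detectable values. The outcome is the mean log viral load over 7 on-treatment swabs, expressed in SDs of a single swab. All correlations are assumed.

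**Base factor.** (1.960 + 0.842) × √(2/30) = 0.723 SD. The detectable difference is 0.723 × √v, where v is the variance of the patient mean. Adjustment for baseline reduces v by c², where c is the average correlation of the baseline with the on-treatment swabs. The equivalent number per arm is 30 × v(unadjusted)/v(adjusted).

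**A. Decaying correlation, added swab.** Baseline on Day 1, then Days 3, 6, …, 21. The correlation between two swabs is d to the power of the days between them.

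| Daily d (3-day value) | v unadjusted | c | v adjusted | Detectable difference, SD | Like n per arm |
|---|---|---|---|---|---|
| 0.90 (0.73) | 0.551 | 0.380 | 0.406 | 0.54 → 0.46 | 41 |
| 0.80 (0.51) | 0.356 | 0.186 | 0.321 | 0.43 → 0.41 | 33 |
| 0.70 (0.34) | 0.260 | 0.106 | 0.248 | 0.37 → 0.36 | 31 |

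**B. Constant correlation r, added swab.** v = (1 + 6r)/7 unadjusted and v − r² adjusted.

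| r | v unadjusted | v adjusted | Detectable difference, SD | Like n per arm |
|---|---|---|---|---|
| 0.3 | 0.400 | 0.310 | 0.46 → 0.40 | 39 |
| 0.5 | 0.571 | 0.321 | 0.55 → 0.41 | 53 |
| 0.7 | 0.743 | 0.253 | 0.62 → 0.36 | 88 |

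**C. No added swab: the first of the 7 scheduled swabs is moved before the first rinse.** The outcome is then the mean of 6.

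- Constant r = 0.3, 0.5, 0.7: v = (1 + 5r)/6 − r² = 0.327, 0.333, 0.260, so 0.41, 0.42, 0.37 SD. This is nearly the whole gain of B.
- Decay at 3-day spacing, d = 0.90, 0.80, 0.70: adjusted v = 0.449, 0.370, 0.289, so 0.48, 0.44, 0.39 SD. Against 0.54, 0.43, 0.37 SD with all 7 swabs unadjusted, that is a gain in the first case and a slight loss in the other two.
- Decay at 2-day spacing (Days 1, 3, …, 21, 11 swabs): 0.53, 0.42, 0.35 SD unadjusted becomes 0.47, 0.41, 0.36 SD. The loss at d = 0.80 disappears; a small one remains at 0.70.

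**D. Worst case for the covariate.** If the baseline predicts nothing, two arms of 30 leave a standard-error ratio of about √(1 + 1/56) = 1.009, a cost of about 1%. At constant correlation, adjustment breaks even at r of about 0.06.

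**E. Undetectable values.** A simulation (6,000 trials; load starting 2 SD above the detection limit, falling 0.15 SD per day and floored at the limit; about 40% of later swabs undetectable) gave these ratios of adjusted to unadjusted standard error: 0.93 for decay with d = 0.80 (0.96 without the floor), and 0.91, 0.78 and 0.64 for constant r = 0.3, 0.5 and 0.7 (0.88, 0.75 and 0.59 without the floor). Under these settings the gain survives.

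**The case against.** **The absence cannot be confirmed.** The swab sentence defers to the Instruction Sheet, where one would expect the timing of the first swab. The 4-hour rule can also be read as spacing after rinses already done, which does not forbid a swab before the first one. This stands: the claim is that the available text does not secure a pre-rinse load, not that the plan excludes one.

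**Nothing is biased or short of a target.** A reader might infer that a missing baseline invalidates Aim 2 or leaves the trial underpowered. The documents support neither. Randomisation protects the comparison, and a pilot with no power target has no target to miss.

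**The largest figures are fragile.** A reader might take 53 or 88 per arm as the expected gain. Those figures need correlation that stays constant over 21 days of an acute infection, and nothing in the documents supports that. Decay gives 31 to 41.

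**The extra swab may be unnecessary.** Under constant correlation, moving the first swab does almost as well. The added swab earns its place mainly when correlation decays at 3-day spacing, where it improves on the moved swab by 0.02 to 0.03 SD.

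**The comparator is not in the protocol.** The mean of 7 swabs is an illustration, because section 10.0 names no model. The unspecified analysis is the more basic gap. Even so, a covariate cannot be used unless the swab exists.

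**The baseline would be collected after randomisation by patients who know their arm.** It is valid only if no rinse came first. Adjusting for a swab taken after a rinse could introduce bias into an otherwise unbiased comparison. This stands, and the fix needs a safeguard.

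**Conclusion.** The point holds as an inexpensive gain in precision, not as an error. As written, the available text secures no quantified pre-rinse viral load, and section 10.0 plans no baseline adjustment. Under decaying correlation, the more natural assumption for an acute infection, an added pre-rinse swab shrinks the detectable difference by about 0.01 to 0.08 SD; the gain is small if decay is fast. Constant correlation of 0.3 to 0.7 gives an upper range, from 0.46-0.62 SD down to 0.36-0.41 SD. These sizes rest on assumed correlations, an assumed summary of 7 swabs, and one pairwise comparison without multiplicity adjustment. The point would reduce to the missing covariate if the Instruction Sheet already sets a first swab before the first rinse.

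**What to change.** 1. Confirm what the Instruction Sheet says about the first swab. If it already precedes the first rinse in every arm, only steps 3 and 4 are needed.
2. Otherwise, have all three arms take one kit swab on kit arrival, before any rinse, and define it as baseline. Either move the first scheduled swab there (no added samples, but possibly a slight loss if correlation fades quickly) or add one swab.
3. Record the clock time of that swab and of the first rinse. State that a swab taken after a rinse is not used as baseline: treat the baseline as missing and keep the patient in the analysis.
4. Pre-specify in section 10.0 that the Aim 2 viral-load comparison is adjusted for the pre-rinse log viral load, and name the model.

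Leave the rinse regimen and the 4-hour rule for later swabs unchanged.

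**Cost.** A line or two each in section 6.0, section 10.0 and the Instruction Sheet. No extra visit is needed, since the kit is already delivered at the start and swabs are retrieved at the end. An added swab means up to 90 more qPCR runs. The schedule implies 90 × 7 = 630 to 90 × 11 = 990 runs, so the increase is 90/990 = 9% to 90/630 = 14%, plus any sequencing or cytokine work chosen for those swabs. At 3-day spacing the total becomes 8 swabs per patient, within the 7 to 11 that the schedule already allows.

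### The sample-level microbiome and data-integration tests name no independent unit, so factors fixed per patient may be tested as if repeated swabs were independent

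*Combined protocol and SAP*

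**What the plan says.** Sampling is repeated by design. Section 6.0 states that "All patients will perform nasal swabs every 2-3 days" over Days 1-21, and Aim 1 in Section 2.0 is to define the "longitudinal SARS-CoV-2 mucosal immune response, microbial load, and viral load in the nasopharynx".

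The inference is described per sample, in three paragraphs of Section 6.0:

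- **16S Sequencing** describes diversity within and between samples and names "non-parametric multivariate analysis of variance (NP-MANOVA") as one example of its tests of community structure. It adds: "We will determine if specific microorganisms correlate with viral SNPs, disease severity, and/or host gene expression".
- **Metatranscriptomics Sequencing** maps transcripts, with "their relative abundance determined from the various samples and time points". Transcripts found to track host or microbiome response "in the samples selected for RNA-seq will be investigated across the entire sample set using qRT-PCR".
- **Data integration** computes distances among ordinal phenotypes, to be "matrix regressed in conjunction with the distance matrices between the samples". It then enters all the omics distance matrices together as predictors of the phenotype distance matrix. "Significance and effect sizes of the regression coefficients will be reported".

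Section 10.0 gives 90 patients in three arms, routine software and a 95% confidence level. No section gives a patient term, a permutation unit or strata, a summary per patient, or a rule of one swab per patient.

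**The concern.** Swabs from one patient resemble each other. Arm is fixed per patient; viral genotype and severity may be too. For such factors the information lies in 90 patients, not in several hundred swabs. A permutation test that shuffles swabs freely compares the observed statistic with a reference distribution that has lost the within-patient resemblance and is therefore too narrow. Ordinary differences between people can then be reported as associations of the microbiome with arm, genotype or severity. Aim 2 asks what the rinses do to inflammation and secondary bacterial load, so a comparison of nasal flora by arm is a natural use of these tests.

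For change over time the error can go either way: patient-to-patient variation makes free permutation conservative, and serial correlation pushes it towards over-rejection.

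**Working it through.** The plan states no power, effect size or error rate for these analyses, so there is no figure of its own to reproduce.

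**Inputs from the document.** 21 days and a swab every 2-3 days (Section 6.0); 90 patients in 3 arms (Sections 6.0 and 10.0); 5% level, implied by the 95% confidence level (Section 10.0).

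**Assumed, not in the document.** Within-patient correlation (ICC) of 0.1/0.3/0.5; number of swabs m entering a test; number of independent axes; serial correlation.

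**Step 1, swabs collected.** 21/3 = 7 to 21/2 = 10.5 per patient. At 7 swabs there are 90 × 7 = 630 samples and 630 × 629/2 = 198,135 sample pairs, against 90 × 89/2 = 4,005 patient pairs.

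**Step 2, approximation for a three-level patient factor on one axis.** DE = 1 + (m − 1) × ICC, and the false-positive rate is P(χ² on 2 df > 5.991/DE) = exp(−5.991/(2 × DE)). For m = 7 and ICC 0.3, DE = 2.8 and the rate is exp(−1.070) = 0.343.

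| Swabs entering | ICC 0.1 | ICC 0.3 | ICC 0.5 |
|---|---|---|---|
| 1 | 0.05 | 0.05 | 0.05 |
| 2 | 0.066 | 0.100 | 0.136 |
| 3 | 0.082 | 0.154 | 0.224 |
| 7 | 0.154 | 0.343 | 0.473 |
| 10 | 0.207 | 0.445 | 0.580 |

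Simulating NP-MANOVA on one axis with m = 7 gave 0.139/0.337/0.464, in agreement.

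**Step 3, NP-MANOVA on 5 axes.** Null simulation, 30 patients per arm, m = 7, Euclidean distance, 1,000 replicates, 199 permutations. Free permutation rejected 0.311/0.771/0.916; repeat runs gave 0.31-0.34/0.76-0.77/0.92-0.96. Whole-patient permutation gave 0.039-0.062; shorter repeats lay between 0.035 and 0.08. With only 2 swabs per patient, free permutation on 5 axes gave 0.09/0.15/0.26.

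**Step 4, matrix regression with a four-level severity fixed per patient.** m = 7, 5 axes, 99 permutations. Free permutation rejected 0.043/0.177/0.352 in 600 replicates and 0.087/0.220/0.353 in a separate run of 150. Whole-patient permutation gave 0.033-0.058 across the runs.

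**Step 5, matrix regression with severity scored by day.** 5 axes, serial correlation 0.3. The result depends on how stable severity is within a patient:

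| Severity ICC | Omics ICC 0.3 | Omics ICC 0.5 |
|---|---|---|
| 0.3 | about 0.06 | about 0.08 |
| 0.6 | 0.11-0.13 | 0.16-0.20 |

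At severity ICC 0.3, whole-patient permutation gave 0.037-0.062.

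**Step 6, early versus late swabs** (first 4 against last 3, ICC 0-0.5, 2,000 replicates; the contrast was also run with 4,000).

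| Serial correlation | Free permutation | Within-patient permutation |
|---|---|---|
| 0 | 0.007-0.048 | 0.047-0.049 |
| 0.3 | 0.018-0.092 | 0.098-0.116 |
| 0.5 | 0.021-0.105 | 0.152-0.157 |

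One early-minus-late contrast per patient with random sign-flipping held 0.044-0.055 throughout (4,000 replicates). That check used a numeric feature, not a distance matrix.

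**The case against.** The strongest reply is that this is silence, not a stated error. A reader might infer that the plan treats swabs as independent; it does not say so. The Data integration paragraph begins from donors whose viral genome, severity and microbial diversity are known, which could mean one record per donor. The RNA-seq work covers selected samples, with no number per patient. The 16S paragraph also cites earlier work not available here, although as worded that citation covers isolation and sequencing rather than testing. All of this stands as a limit, but none of it supplies a unit, and the sample-level reading is a natural one in a longitudinal study.

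A reader might also infer that all the omics tests are distance tests on 7-10 swabs per patient. That goes too far. Seven to ten is the number collected; RNA-seq enters a distance matrix only in the integration step; and alpha diversity and taxon correlations are not distance tests.

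Nor do the highest rates belong to the matrix regression. They come from NP-MANOVA, which the plan gives only as an example and does not tie to arm. The matrix regression shows little or no inflation at ICC 0.1 and clear inflation from 0.3.

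Finally, this is a pilot for which Section 10.0 disclaims a power analysis. That lowers the stakes, but a pilot that reports significance still needs a valid reference distribution.

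**Conclusion.** The concern holds conditionally. If more than one swab per patient enters a test and swabs are permuted as if independent, tests of factors fixed per patient reject too often. The inflation ranges from slight (0.07 with 2 swabs, one axis, ICC 0.1) to severe (about 0.92 for NP-MANOVA with 7 swabs, 5 axes, ICC 0.5). Every ICC, the number of axes and the number of swabs entering are assumptions. With one swab per patient the problem does not arise.

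Two reassurances that a reader might draw are not supported. Scoring severity by day does not make the inflation small in general: it was small at a severity ICC of 0.3 but reached 0.11-0.20 at 0.6. Nor can the viral-load comparison be called unaffected. Titers come from the same repeated swabs, and neither the qPCR paragraph nor Section 10.0 gives a model for them, so the documents settle it neither way.

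The plan should be amended on this point before these tests are run.

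**What to change.** Add to Section 6.0:

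1. The patient is the independent unit in the 16S, RNA-seq and data-integration tests.
2. Factors fixed per patient are tested, in NP-MANOVA and in the matrix regression, by permuting whole patients so that all swabs of a patient move together, or on one summary per patient.
3. The same holds where severity is scored by day. Where series differ in length, as they will when hospitalization ends follow-up under Section 9.0, use one summary per patient.
4. Change over time is tested on one early-minus-late contrast per patient of a defined numeric feature (for example alpha diversity, a taxon abundance or an ordination score), for instance by sign-flipping, and not by free permutation of swabs.
5. How many swabs per patient enter each assay, and whether severity is recorded per patient or per day.

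The cost is a few sentences and a permutation option; no new samples are needed. Fewer exploratory associations will reach significance, and patients without both an early and a late swab drop out of the time contrast.
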